10.18.3 Electrocardiogram

A 12-lead ECG (including HR and cardiac intervals: PR, QRS, QT, QTcF, and QTcB) will be performed after the subject has rested for at least 5 minutes in the supine position. The Investigator will perform an overall evaluation of the ECG for safety purposes and the recording will be reported as 'normal', 'abnormal CS', or 'abnormal NCS'. Abnormalities of clinical significance will be reported as AEs. Repeat measurements will be performed, if needed. If required, the ECG may be reviewed by a specialist to evaluate for suspected abnormalities.

10.18.4 Transvaginal Ultrasound

A TVU will be performed outside menstruation during the Screening Period to identify clinically significant gynecologic condition as defined in the exclusion criteria

The Investigator will read the scan at

Screening and decide whether the subject is eligible for the study or not.

10.18.5 Routine Laboratory Evaluations

Blood and urine samples will be collected for routine clinical laboratory safety evaluations during the study are presented in Table 4.

Additional laboratory safety evaluations will be performed at other times, if judged clinically appropriate, or if the ongoing review of the data suggests a more detailed assessment of laboratory safety evaluations is required. Any changes to the scheduled times of laboratory safety tests will be agreed with the Sponsor and documented in the TMF.

The Investigator will perform a clinical assessment of all laboratory safety data.

Table 4 Routine Laboratory Evaluations

Hematology: Hemoglobin Hematocrit Platelet count Red blood cell (RBC) count Reticulocyte count	Mean corpuscular hemoglobin (MCH) Mean corpuscular hemoglobin concentration (MCHC) Mean corpuscular volume (MCV) White blood cell (WBC) count and differential	
Biochemistry: Alkaline phosphatase (ALP) Aspartate aminotransferase (AST) Alanine aminotransferase (ALT) Gamma-glutamyl transpeptidase (GGT) Potassium Sodium Chloride Inorganic phosphate Glucose Urea Bilirubin (direct and total)	Cholesterol Triglycerides High density lipoprotein-cholesterol (HDL-C) Low density lipoprotein-cholesterol (LDL-C) Protein (total) Albumin Creatine kinase Creatinine	
Coagulation: Prothrombin time International normalized ratio	Activated partial thromboplastin time	
Urinalysis: Specific gravity, pH, protein, glucose, ketones, urobilinogen, hemoglobin Microscopic examination ¹		

¹ Performed only if required, based on urinalysis results

Blood and urine samples will be performed by the Central Laboratory using standard methods. Procedures for the handling of samples will be described in full in a separate document.

10.18.6 Total blood volume

The approximate total blood volume taken per subject is given in Table 5.

Table 5 Blood Volumes

Procedure	Sample volume (mL)	No. of samples	Total volume (mL)
Hematology	3.0	10	30.0
Biochemistry	4.0	10	40.0
Coagulation	3.0	10	30.0
PK	2.5	9	22.5
Measurement of anti-MT-2990 antibody	5.0	5	25.0
Biomarker (in serum)	7.0	5	35.0
	•	Overall total	182.5

Additional or repeat safety laboratory samples may be taken during the study if required by the Investigator.

10.20 Pharmacokinetic Assessments

Blood samples will be collected via cannulation or direct venipuncture in a suitable forearm vein. The actual date and time of each blood sample collected will be recorded in the subject's eCRF.

For each PK assessment, 1 blood sample of approximately 2.5 mL will be collected to ensure there is sufficient serum for primary and contingency samples. Sample handling details will be described fully in a separate document.

10.21 Immunogenicity Assessments

[figure not shown]
Blood samples will be collected via cannulation or direct venipuncture in a suitable forearm vein. The actual date and time of each blood sample collected will be recorded in the subject's eCRF.

For each immunogenicity assessment, 1 blood sample of approximately 5 mL will be collected to ensure there is sufficient serum for primary and contingency samples. Sample handling details will be described fully in a separate document.

11 STUDY DRUG/TREATMENT

11.1 Investigational Medicinal Product

11.1.1 Drug Product

11.1.2 Study Drug Supply

MT-2990 vials will be labeled and released according to GMP. All labeling will comply with applicable regulatory requirements. The Sponsor will provide all required release documentation for the finished product before it is dispatched.

The Sponsor will provide MT-2990 10 mL clear glass vials, fitted with fluoropolymer-faced butyl rubber stoppers and aluminum seals with pale green plastic flip-off caps to each site, for for the duration of the subject's participation in the study. The unblinded pharmacist/trained designee will dispense a sufficient quantity of MT-2990 10 mL vials according to the subject's body weight consistent with each subject's dosage requirement and study visits according to the protocol.

Specifically, MT-2990 (each will be dispensed in a manner consistent with each subject's dosage requirement.

which will be used for dispensing MT-2990 in a manner consistent with each subject's dosage requirement or will be used as placebo, will be sourced from a commercial supplier.

11.1.3 Formulation, Packaging, Site Storage, and Labeling

MT-2990 will be provided to the study sites in labeled vials. MT-2990 should be stored according to the IMP clinical label and should be stored according to commercial labeling.

The labeling of MT-2990 10 mL vial (dispensing) will comply with applicable regulatory requirements. Appropriate volumes (according to the subject's body weight) of MT-2990 concentrate for solution for infusion will be withdrawn from the vial(s), and added to The dispensed

MT-2990 and placebo

without MT-2990) will be labeled. The dispensing, labeling and release will be performed and documented according to local requirements and procedures. The labeling will comply with applicable requirements.

Required study site documentation for MT-2990 vials will include, but may not be limited to, the following information:

- Receipt date
- Description of medication package, and medication product
- Lot number or code/Batch number or code
- Expiration and manufacturing dates
- Dispensing information
- Investigation New Drug number
- Certificate of compliance

11.1.4 Shipping, Receipt, Handling and Storage

On receiving a shipment of
at the Investigator site, the unblinded pharmacist/trained designee will conduct an inventory
check and complete a supplies-receipt document via the Interactive Web-based Response
System (IWRS), the original of which will be retained at the Investigator site. The unblinded
pharmacist/trained designee will maintain a record of all
received and returned

at the Investigator site will be stored according to the conditions stated on the IMP clinical label and commercial label, respectively, in a locked, restricted-access area. The MT-2990 concentrate for solution for infusion should be allowed to reach ambient temperature before removing the required volume from the single use vial. A temperature log recording the daily maximum/minimum temperature of the storage area will be maintained (including weekends). Any storage temperature deviations of will be reported to the Sponsor.

11.1.5 Dispensing

On each dosing occasion, a record of the "Study medication",

which will be

dispensed to each subject, will be maintained by the unblinded pharmacist/trained designee on an accountability log. Any opened vials will not be re-used.

At each visit, the unblinded pharmacist/trained designee will prepare with the subject allocated dose.

should be used within 4

hours at room temperature or within 24 hours at 5°C (±3°) of its preparation. Study

Protocol MT-2990-A01

Confidential

Page 59 of 103

110100011111 2550 1101
medication will be administered
The Investigator or designee will be blinded to the study medication content and provide the subject with the dose pharmacist/trained designee. A record of the study medication infused to each subject will be maintained by the unblinded pharmacist/trained designee on a Medication Accountability Log Refer to instructions in the pharmacy manual.
11.1.6 Study Medication Accountability
The unblinded pharmacist/trained designee must maintain an accurate record of the shipment. During the study, the unblinded pharmacist/trained designee will record the quantities of study medication dispensed on an Accountability Log. All used vials and infusion bags must be retained for the purpose of drug accountability. The accountability (drug reconciliation) will be noted by the unblinded monitor during site visits and at the completion of the study. Study medication is to be used only for this Protocol and not for any other purpose.
11.1.7 Disposal and Destruction
At study close-out, and as appropriate during the course of the study, the unblinded study monitor will return all used and unused packaging, and a copy of the completed Medication Accountability Log to the Sponsor's designated facility or to the address provided in the Investigator Binder at each site.
may be destroyed at the designated Sponsor facility or third party, as appropriate. Sites with documented drug destruction procedures and facilities may destroy drug on site with sponsor approval. Confirmation of destruction will be provided to the Sponsor.
A Sponsor designated facility will arrange for all used/unused MT-2990 vials and packaging to be destroyed according to local procedures and used/unused to be destroyed after follow-up weighing upon return to the pharmacy according to local procedures once permission has been given by the Sponsor. Confirmation of destruction will be provided to the Sponsor.
Permission to return will only be given after all reconciliation has been completed and any queries closed. Authorization to destroy will be given when the Clinical Study Report (CSR) is signed, or as agreed with the Sponsor.
11.2 Dosing
The injection will be administered via of approximately 250 mL, at a dose of MT-2990 or placebo, over a period of approximately 45 minutes (± 5 minutes). The injection will be administered via 18 to 21-gauge cannula through a peripheral line. Following administration of study drug, will be flushed with ensure that the entire dose is administered. An unblinded pharmacist/trained designee will reconstitute the MT-2990 injection for administration. MT-2990 injection will be dosed on an mg/kg basis. The dose to be delivered will be controlled by adjusting the total volume of injection.

Placebo is and the volume of dose to be delivered should be same as with the total volume of MT-2990.

A description of the study medication dispensed are given in Table 6 and Table 7.

 Table 6
 Investigational Medicinal Product

	MT-2990 (Vial)
Dosage form	Concentrate for solution for infusion
Description	
Strength	
Storage conditions	The MT-2990 vials must be stored according to the conditions stated on the IMP clinical label. Keep the vials in the original carton until infusion preparation. The MT-2990 concentrate for solution for infusion should be allowed to reach ambient temperature before removing the required volume from the single use vial.

Table 7 Study Medication

	MT-2990	Placebo
Dosage		Placebo to match active bag dose
Route of administration		
Treatment duration		
Dosing instructions	The MT-2990 solution should be diluted with Infusion should take place over approximately 45 minutes (± 5 minutes).	Infusion should take place over approximately 45 minutes (± 5 minutes).
Storage conditions (after dilution)	Within 4 hours at room temperature or 24 hours at 5°C (±3°) after dilution	Store according to commercial labeling

11.3 Compliance

Study medication will be administered by according to the Protocol requirements, by designated qualified study personnel at the study site. The Investigator, or suitably qualified staff member, will supervise the administration of study medication and the exact time of dosing will be recorded in the subject's eCRF.

The prescribed dosage, dose duration, timing and mode of administration of study medication may not be changed. Any departures from the intended regimen must be recorded in the subject's eCRF.

11.4 Subject identification

At Screening, the IWRS will assign each subject a unique Subject Identifier. The format of the unique Subject Identifier is A01-123-00345 where 123 is the 3-digit site number and 00345 is the 5-digit subject number, assigned uniquely, and sequentially to subjects across the study. The Subject Identifier will be used to reference the subject during the whole duration of the study. At the point of randomization, each subject will receive a unique Randomization Number. Both the Subject Identifier and the Randomization Number will be documented in the subject's source documents. The Subject Identifier will be recorded on study medication labels and other documentation.

A list identifying the subjects by their unique Subject Identifier and Randomization Number will be kept in the Investigator Site File.

11.4.1 Procedures for Assigning Subjects to Treatment Groups

Randomization will take place after confirmation of inclusion/exclusion criteria prior to the administration of study medication on Day 1. Subjects will be randomly allocated to 1 of 2 treatment groups (MT-2990 or placebo) in a ratio of 1:1, according to an IWRS.

[figure not shown]
11.5 Maintenance of the Study Blind and Unblinding

Treatment will be double-blind; that is, neither the subject nor the Investigator site personnel except for unblinded pharmacist/trained designee will know which treatment is being taken. MT-2990 and placebo doses will be indistinguishable in volume and appearance in order to maintain the blind. Each subject's treatment will be labeled with a unique Subject Number, Initials, visit number and date. The IWRS will be used to hold treatment codes for each subject. The codes will only be accessible to authorized IWRS users. The IWRS should not normally be accessed with a request to break the treatment code for reasons other than safety or in an emergency. Should the Investigator wish to break the code for such reasons, he/she should ideally consult the Sponsor in advance. If this is not possible, the Investigator may access the IWRS to obtain the treatment code and provide the system with the reason for breaking the blind. The Sponsor should be notified as soon as possible thereafter. If the blind is broken for any individual subject, the subject must be withdrawn from the study, and any procedures accompanying withdrawal should be performed (refer to Table 2).

The Sponsor will be unblinded after Week 16 (Visit 9), while the Sites and subjects will remain blinded until the end of the Extended Follow-up period at Week 38 (Visit 11).

Pharmacokinetic analysis will only be performed on samples from subjects receiving MT-2990; unblinded randomization codes will be given to the PK laboratory.

An electronic list of randomization codes will be retrieved from IWRS and transferred to the Sponsor at the end of the study.

12 ADVERSE EVENT MANAGEMENT

All AEs and SAEs will be recorded in the source documents. All SAEs that occur from the time written ICF is obtained until the end of the Double-blind Treatment Period (Visit 9), and all AEs that occur from Day 1 until the end of the Double-blind Treatment Period (Visit 9) will be recorded in the eCRF. Even if the AE is assessed by the Investigator as not related to study medication, its occurrence must be recorded in the source documents and eCRF. AEs will be classified as 'treatment-emergent' if they arise following the administration of study medication or if a predose illness increases in severity following dosing.

At each study visit, after the subject has had an opportunity to spontaneously mention any problems, the Investigator should inquire about the occurrence of AEs. The questioning should be open-ended and nonleading.

Post each study drug infusion, subject should be observed for approximately 60 ± 10 minutes. During this period, vital signs must be obtained at 15 ± 5 minutes, 30 ± 5 minutes and 60 ± 10 minutes. A patient instructions sheet will be provided to all subjects with instructions to observe and report all possible adverse events such as infusion related or infections in particular.

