7 STUDY DESIGN

7.1 Overall Study Design

7.1.1 Study Methodology

This is a Phase 2, randomized, double-blind, placebo-controlled study, stratified by moderate or severe pain to evaluate safety and efficacy of MT-2990 in women with endometriosis-associated moderate to severe pain. Approximately 76 subjects will be randomized into the study, with approximately 38 subjects in each treatment arm. The approximate duration of the study per subject is 52 weeks, inclusive of the Screening period, Double-blind Treatment period, and the Extended Follow-up period.

Following the Screening period, eligible subjects who have met all the eligibility criteria and have moderate or severe nonmenstrual pelvic pain, and dysmenorrhea will be randomized into the study. Approximately 38 subjects per arm will be enrolled. Subjects will be randomly allocated to 1 of 2 treatment groups (placebo or MT-2990 in a ratio of 1:1.

All efficacy and safety measures will be collected during the 16-week Double-blind Treatment period.

End-of-treatment (EOT) will occur at Week 12 (Visit 7) and primary and secondary efficacy endpoints will be assessed at the Week 16 (Visit 9) visit. Subjects who discontinue from the study will complete the procedures for Visit 9 within 10 days of discontinuation (or as soon as possible after the site becomes aware of the discontinuation).

During the Extended Follow-up period, visits will be conducted via a telephone call at Week 27 (Visit 10) and at Week 38 (Visit 11).

The Sponsor will be unblinded after Week 16 (Visit 9), while the Sites and subjects will remain blinded until the end of the Extended Follow-up period at Week 38 (Visit 11). During the study, database will be locked twice: at Week 16 (Visit 9) to assess safety and efficacy, and at Week 38 (Visit 11) to assess other outcomes during the Extended Follow-up period.

There will be 3 interim assessments for safety. The first interim assessment for safety will be performed when 20 subjects are randomized and have completed the Week 2 visit. The second interim assessment for safety will be performed when 50% of the subjects are randomized and have completed the Week 4 visit. The third interim assessment for safety will be performed when 50% of the subjects are randomized and have completed the Week 16 visit.

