Serious adverse events (SAE) will be collected from the time of signing the ICF. All adverse events (AEs) will be collected from Day 1 through the Double-blind Treatment period (Visit 9). All fractures will be collected as events of special interest (AESI).

Blood and urine samples will be obtained at protocol prespecified time points for chemistry, hematology, and PK. Subjects will be required to undergo TVU during Screening and at the Week 16 visit.

The study does not require a laparoscopy procedure or dual-energy x-ray absorptiometry (DEXA) scan at any time during or after the study. All laparoscopic procedure data will be collected from the most recent laparoscopy procedure as well as any clinically indicated laparoscopy performed during the Double-blind Treatment period and Extended Follow-up period.

If available, data will be collected from the most recent DEXA scan (within 1 year of Screening) and any DEXA scan conducted during the Double-blind Treatment period and Extended Follow-up period.

The study design is presented in Figure 1.

[figure not shown]

Figure 1 Study Design Schematic

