7.2.1 Risk:Benefit Statement

Treatment of moderate to severe pain related to endometriosis is a significant unmet need. Young women at childbearing age develop endometriosis related pain and other complications which effects their productivity at peak age.

The current study will evaluate the effect of MT-2990 on treatment of moderate to severe endometriosis related pain. This study will evaluate if MT-2990 may treat the endometriosis related pain.

MT-2990 is a human IgG1 monoclonal antibody that highly and specifically binds to IL-33 among IL-1 family molecules. It is under investigation for the potential clinical benefits for the treatment of moderate to severe endometriosis-related pain in women with surgically diagnosed endometriosis.

[figure not shown]
The overall nonclinical safety data and profile is supportive of the clinical use of MT-2990 in human clinical trials. Nonclinical studies have demonstrated no significant toxicity of MT-2990.

In the 1 clinical study conducted to date, single doses of MT-2990 were considered to be safe and well tolerated in healthy male subjects. No deaths, SAEs, AEs leading to withdrawal, or severe TEAEs occurred during the study.

The Sponsor will undertake all reasonable measures, to minimize the risk to subjects. Subjects will receive no further dosing if they meet any of the withdrawal criteria listed in Section 8.5.

This study will provide additional efficacy and safety information on the risk:benefit profile of MT-2990.

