12.2 Adverse Events of Special Interest

AESIs will be collected for the following:

All bone fractures

All AESIs (including event management and evaluation) will be recorded and reported similar to SAEs as described in Section 12.8. MT-2990 does not have any hormonal effects and is not anticipated to have any impact on bone mineral density. However, this population has been exposed to other hormonal treatments prior to study entry, increasing the risk of osteoporosis and possible fractures.

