12.7 Recording and Reporting of Adverse Events

All AEs, regardless of the relationship to study medication, occurring from Day 1, will be obtained from a subject until the end of the Double-blind Treatment Period (Visit 9) or the withdrawal of the subject from the study will be recorded.

NOTE: Elective hospitalization or procedure/surgery planned before subject enrollment for a preexisting medical condition does not constitute an AE unless the underlying disease or condition worsens after Day 1.

All AEs will be recorded on an AE form in the eCRF. Reports should contain a description of the event, date and time of onset, date and time of resolution, severity, treatment required, relationship to study medication, action taken with the study medication, outcome and whether the event is classified as serious.

The Investigator will evaluate the severity of the AEs (as defined in Section 12.4) and will assess the causality between the AEs and the study medication (as defined in Section 12.5).

Pre-existing illnesses, which started prior to entry and are still ongoing at the start of the study, will not be considered AEs unless they worsen during the Double-blind Treatment period. Pre-existing conditions will be recorded as medical history.

If the Investigator becomes aware of any new safety information, or any safety information, which appears to be either study or study medication related after the Double-blind Treatment period, then they must notify the Sponsor immediately. This information does not require reporting of an AE on the eCRF, but should still be communicated to the Sponsor.

12.8 Recording and Reporting of Serious Adverse Events or Adverse Events of Special Interest

All SAEs occurring from the time written ICF is obtained from a subject until the end of the Double-blind Treatment Period or the withdrawal of the subject from the study must be reported to the Sponsor or the designee using the SAE/AESI Form in Clinical Study within 24 hours of the Investigator becoming aware of the SAE. All SAEs and AESI must also be entered in the AE section of the eCRF within 24 hours.

SAE report should be completed as thoroughly as possible, including an assessment of causality. All such reports will identify subjects by unique code numbers assigned to the study participants, rather than by the subjects' names, personal identification numbers, or addresses.

The reporting contact for SAEs/AESI is as follows:

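### eCRF entry of SAEs ends at Week 16 although follow-up calls run to Week 38; the fracture window is unstated, and no complete by-arm table of late SAEs is visible

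*Protocol*

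**What the plan says.** **SAEs.** Protocol section 12 limits eCRF recording to "All SAEs that occur from the time written ICF is obtained until the end of the Double-blind Treatment Period (Visit 9"). Section 12.8 ties expedited reporting to the same endpoint: events up to the end of the "Double-blind Treatment Period or the withdrawal of the subject from the study must be reported to the Sponsor or the designee". Section 7.1.1 gives SAE collection a start, at consent, and no end.

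**All AEs.** Section 7.1.1: "All adverse events (AEs) will be collected from Day 1 through the Double-blind Treatment period (Visit 9").

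**After Visit 9.** Section 12.7 requires immediate notification if the investigator learns of new safety information, then adds: "This information does not require reporting of an AE on the eCRF, but should still be communicated to the Sponsor".

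**Fractures.** Section 12.2 makes bone fractures the only AESI and says: "All AESIs (including event management and evaluation) will be recorded and reported similar to SAEs as described in Section 12.8". Section 7.1.1 says that all fractures are collected and gives no end date.

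**Follow-up.** Section 7.1.1: "visits will be conducted via a telephone call at Week 27 (Visit 10) and at Week 38 (Visit 11"). Sections 7.1.1 and 11.5 unblind the Sponsor after Week 16 and keep sites and subjects blinded to Week 38. A second database lock at Week 38 is for other outcomes of the Extended Follow-up period. Section 7.1.1 also collects data from "any DEXA scan conducted during the Double-blind Treatment period and Extended Follow-up period", and from clinically indicated laparoscopies over the same span.

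**Analysis.** Protocol section 14.3.4.4 and SAP section 7.1.3.1 call an event treatment-emergent if it starts, or worsens, after the first dose; neither sets an end. SAP section 8.3.1 tabulates serious TEAEs and treatment-emergent AESIs, with no separate table for the Extended Follow-up period.

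**The concern.** The plan keeps subjects in contact, and sites blinded, for 22 weeks after it stops entering serious events in the eCRF. The tables of serious TEAEs and AESIs rest on a definition without an end date but draw on a database that need not hold events after Week 16. A reader of the study report could take those tables as complete for the study when they are not.

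The setting adds weight. Section 7.2.1 refers to one earlier clinical study, in which "single doses of MT-2990 were considered to be safe and well tolerated in healthy male subjects". The present trial gives repeated doses to women, so there is little earlier experience against which to judge a delayed serious event. Late events would reach a Sponsor that already knows the treatment codes, as individual notifications rather than as a data set collected the same way in both arms.

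**Working it through.** **Inputs**
- Four doses, one every four weeks (SAP section 7.1.1.2). Infusion visits are Visits 2, 5, 6 and 7 (Protocol section 10.18.2), and Visit 7 is Week 12 (section 7.1.1). The last dose is therefore at Week 12.
- Nominal days (SAP section 7.3): Week 12 = Day 85, Week 16 = Day 113, Week 38 = Day 267.
- 38 subjects per arm randomized, 28 per arm after 25% drop-out (Protocol section 14.1). These figures reproduce: a two-sided 5% t-test with difference 0.5 and SD 0.65 has power 0.807 at 28 per arm, and 28 / 0.75 = 37.3, rounded up to 38.

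**Coverage after the last dose**
- Last dose to end of eCRF entry: (113 − 85) / 7 = 4 weeks.
- End of entry to last call: (267 − 113) / 7 = 22 weeks.
- Last dose to last call: (267 − 85) / 7 = 26 weeks.
- Share outside entry: 22 / 26 = 85% of post-dose follow-up, or 22 / 38 = 58% of the time from first dose.

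For early leavers the window can be shorter still, because section 12.8 also closes it at withdrawal. At the assumed drop-out that is 0.25 × 76 = 19 subjects.

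**Person-time outside entry**
- 38 per arm, no drop-out: 38 × 22 × 7 / 365.25 = 16.0 person-years per arm.
- 28 per arm: 28 × 22 × 7 / 365.25 = 11.8 person-years per arm.

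The documents give no event rate. The table assumes 0.02 to 0.20 serious events per person-year and uses 1 − exp(−rate × person-years) for the chance of at least one event in an arm.

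| Per arm | Assumed rate | Expected events | Chance of at least one |
|---|---|---|---|
| 38 | 0.02 | 0.3 | 27% |
| 38 | 0.20 | 3.2 | 96% |
| 28 | 0.02 | 0.2 | 21% |
| 28 | 0.20 | 2.4 | 91% |

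**A serious event at Week 20, rule by rule**
- SAP section 7.1.3.1: treatment-emergent, since it follows the first dose.
- Protocol sections 12 and 12.8: outside the entry and reporting window.
- Section 12.7: notify the Sponsor, no eCRF entry required.
- SAP section 8.3.1: belongs in the serious-TEAE table by definition, but its data source need not contain it.

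**A fracture at Week 20**
- Section 12.2 points to section 12.8, whose only stated window closes at Visit 9 or withdrawal and names SAEs alone. The next rule there, on entering SAEs and AESIs within 24 hours, has no end date.
- Section 7.1.1 collects all fractures without an end date and DEXA data through Extended Follow-up.
- Whether this fracture is to be entered cannot be decided from the text.

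**The case against.** The strongest reply is that late serious events are not lost. Notification is mandatory, and the unblinded Sponsor can assign each reported event to an arm. Section 12 has the investigator ask about AEs at every study visit and record AEs and SAEs in source documents, without an end date; the two calls are numbered visits. SAP section 8.2 plans time to hospitalization and to surgeries, hospitalization is itself an SAE criterion (Protocol section 12.3), and laparoscopy and DEXA data run to Week 38. All of this stands.

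It rules out two stronger conclusions that a reader might draw:
- **That late serious events cannot be compared by arm.** Notified events can be assigned, and the hospitalization and surgery analyses may pick up some. What is missing is required database entry and a planned complete table.
- **That fracture recording stops at Week 16.** That is only an inference from the cross-reference to section 12.8, and section 7.1.1 points the other way. The supportable statement is that the window is not stated.

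Three further points limit the weight of the concern. The schedule of assessments, the pharmacokinetic background and the dose rationale are not in the available text, so neither the content of the calls nor the length of exposure after Week 12 can be checked; four weeks is one dosing interval. The 85% is a share of calendar time, not of risk. The three-month contraception requirement in section 8.6.2 is a pregnancy precaution and does not define a general safety window. Subjects may also start hormonal contraception after Week 16, which could complicate attribution of late events.

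These points do not remove the eCRF exemption in section 12.7, which is a stated rule and holds whatever the calls ask.

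**Conclusion.** The concern holds in a limited form. SAE entry closes four weeks after the last dose and leaves 22 of the 26 post-dose weeks of follow-up (85%) outside the database. The open-ended treatment-emergent definition does not match that cut-off, the fracture window is unstated, and no complete by-arm table of late SAEs appears in the visible text. Late events do reach the Sponsor, and other planned data may capture some of them.

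The week counts follow from the documents alone. The chance that an arm has at least one event in the gap rests on an assumed tenfold range of rates: 27% to 96% at 38 per arm without drop-out. It shows only that such events are plausible.

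This is a worthwhile, inexpensive improvement. It does not affect the efficacy analysis.

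**What to change.** - In Protocol sections 12, 12.7 and 12.8, extend eCRF entry of SAEs and fractures to Visit 11 and remove the exemption for these two categories. Say what applies to subjects who withdraw early.
- State the fracture window in section 12.2 and align section 7.1.1 with it.
- Confirm in the schedule of assessments that the Week 27 and Week 38 calls ask about SAEs and fractures.
- In SAP section 8.3.1, add a descriptive table of SAEs and AESIs by arm on the Safety population at the Week 38 lock, separating events up to Visit 9 from later ones. Make the treatment-emergent definition agree with the collection window.
- Non-serious AEs may still stop at Visit 9.

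The cost is a short protocol and eCRF amendment, two questions on calls already scheduled, one table, and modest added safety reporting work. With about 38 subjects per arm the table can only be descriptive. The change concerns data capture and leaves treatment and clinical management as they are.
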